13.1	APPENDIX I: EL ESCORIAL WORLD FEDERATION OF NEUROLOGY CRITERIA FOR THE DIAGNOSIS OF ALS	
60		
13.2	APPENDIX II: ALS FUNCTIONAL RATING SCALE – REVISED (ALSFRS-R)	62
13.3	APPENDIX III: COLUMBIA-SUICIDE SEVERITY RATING SCALE - BASELINE	65
13.4	APPENDIX IV: COLUMBIA-SUICIDE SEVERITY RATING SCALE – SINCE LAST VISIT	69
13.5	APPENDIX X: SMARTPHONE USAGE QUESTIONNAIRE	73
13.6	APPENDIX XI EXIT QUESTIONNAIRE: STUDY PARTICIPANT	74
13.7	APPENDIX XII EXIT QUESTIONNAIRE: SITE INVESTIGATOR.....	75

LIST OF ABBREVIATIONS

AE	Adverse Event/Adverse Experience
ALS	Amyotrophic Lateral Sclerosis
ALSFRS-R	Amyotrophic Lateral Sclerosis Functional Rating Scale-Revised
CFR	Code of Federal Regulations
CFR	Code of Federal Regulations
CIB	Clinical Investigator's Brochure
CNS	Central Nervous System
CRF	Case Report Form
CSF	Cerebrospinal Fluid
C-SSRS	Columbia Suicide Severity Rating Scale
DBP	Diastolic Blood Pressure
DSMB	Data and Safety Monitoring Board
eCRF	Electronic Case Report Form
FDA	Food and Drug Administration
FRAP	Ferric Reducing Antioxidant Power
FWA	Federal-wide Assurance
GCP	Good Clinical Practice
GSH	Glutathione
HIPAA	Health Insurance Portability and Accountability Act
ICF	Informed Consent Form
ICH	International Conference on Harmonization
IDE	Investigational Device Exemption
IND	Investigational New Drug Application
IRB	Institutional Review Board
ITT	Intent to treat
KO	Knockout
MOP	Manual of Procedures
MS	Multiple Sclerosis
N	Number (typically refers to subjects)
NDA	New Drug Application
NIH	National Institutes of Health
Nrf2	Nuclear factor erythroid 2-related factor 2
OHRP	Office for Human Research Protections
OHSR	Office of Human Subjects Research
PD	Parkinson's disease
PHI	Protected Health Information
PI	Principal Investigator

QA	Quality Assurance
QC	Quality Control
ROS	Reactive Oxygen Species
SAE	Serious Adverse Event/Serious Adverse Experience
SBP	Systolic Blood Pressure
SI	Site Investigator
SMC	Safety Monitoring Committee
SOP	Standard Operating Procedure
UOx	Urate Oxidase
US	United States
VC	Vital Capacity
WOCBP	Women of Childbearing Potential

PROTOCOL SUMMARY

Study Title

SAFETY OF URATE ELEVATION IN ALS – PHASE II (SURE-ALS2)

Version Number

3.0

Study Indication

Amyotrophic Lateral Sclerosis (ALS)

Phase of Development

2

Rationale for the Study

Amyotrophic lateral sclerosis (ALS) is a fatal, neurodegenerative disease for which there is no cure. Multiple lines of evidence have implicated oxidative stress in the pathophysiology of ALS. Urate (uric acid) is an endogenous antioxidant system, and urate may serve as a major defense against oxidative stress. Urate has emerged as a promising neuro-protectant and therapeutic target based on convergent epidemiological, laboratory, and clinical data in multiple neurodegenerative diseases, most notably Parkinson's disease (PD). In PD, urate elevation has been pursued as a potential therapy by administration of inosine, a urate precursor that is available as an over-the-counter supplement. Administration of inosine results in a predictable elevation of urate levels and has been shown to be safe and well tolerated in PD.

Analysis of ALS databases revealed that higher urate levels are an independent predictor of slower progression and prolonged survival in ALS. However, whether elevating urate in people with ALS would result in better outcomes is unknown.

We have recently concluded a Pilot Study of Inosine in ALS, which was a short, open label, single center study involving 25 subjects. The study showed safety and feasibility of urate elevation in patients with ALS. We are now pursuing a multi-center Phase II trial to confirm these findings with longer exposure time.

Study Design

This is a multi-center, 20-week study of inosine treatment.

Study Objectives and Endpoints

The primary objective of the study is to determine the safety and tolerability of oral administration of inosine (administered daily) dosed to moderately elevate serum urate over 20 weeks.

The primary outcome measures will be

- 1- safety, as measured by adverse events
- 2- tolerability, defined as the ability of subjects to complete the entire 20-week study.

As an exploratory objective, we will test the feasibility and utility of a smartphone application for monitoring symptoms and disease progression in patients with ALS.

Study Location

Up to Three (3) Northeast ALS Consortium (NEALS) Centers in the United States

Number of Planned Subjects

It is expected that approximately 60 subjects will be consented and 30 subjects will be treated in the study.

Study Population

This study will be conducted in subjects who meet the El Escorial criteria of possible, laboratory-supported probable, probable, or definite criteria for a diagnosis of ALS. At screening, eligible subjects must be at least 18 years old and must provide written informed consent prior to screening. Subjects on a stable dose of riluzole and those not taking riluzole, and women of child-bearing age at screening are eligible for inclusion as long as they meet specific protocol requirements. Detailed criteria are described in the body of the protocol.

Treatment Plan

Subjects will be administered oral inosine daily. The dose of inosine will be titrated to obtain serum urate levels of 7 - 8 mg/dL.

Duration of Treatment and Follow-up

Subjects will remain on treatment until the Week 20 visit. Each subject will also have a Week 24 Follow-up Telephone Interview to assess for adverse events (AEs), changes in concomitant medications and to administer the ALSFRS-R.

SCHEDULE OF ACTIVITES

Activity	Screening Visit ¹	Baseline	Week 3, 6 and 9 Phone Call and Urate Test	Week 12	Week 16 Phone Call and Urate Test	Week 20	Week 24 Phone Call	Final Safety Visit (for early study drug discontinuation only)
Visit Names	Visit 1	Visit 2	Visits 3, 4, and 5	Visit 6	Visit 7	Visit 8	Visit 9	
Visit Window	-21 days from Day 0	Day 0	± 3 days	± 3 days	± 3 days	± 3 days	± 3 days	
Written Informed Consent	X							
Inclusion/Exclusion Review	X	X						
Medical History/Demographics	X							
ALS Diagnosis History	X							
Physical Examination	X							
Neurological Exam	X							
Vital Signs ² / Height & Weight ³	X			X		X		X
Screening Labs ⁴	X							
C-SSRS		X		X		X		X
Uric acid level ⁵		X	X	X	X	X		X
Urine alkalization protocol (if needed per protocol)		X		X				
Urinalysis ⁶		X		X		X		X
Basic Metabolic Panel	X							
Safety Labs ⁷		X		X		X		X
ALSFRS-R ⁸		X		X		X	X	X
Pulmonary Function Testing ⁸	X			X		X		X
Concomitant Medication Review	X	X	X	X	X	X	X	X
Adverse Event Review	X	X	X	X	X	X	X	X
Dispense Study Drug		X		X				
Drug Accountability				X		X		X
Exit Questionnaire						X		X
Mobile app installation ¹⁰		X						
Mobile app un-installation ¹⁰						X		X

¹ Screening procedures must be completed within 21 days prior to Baseline Visit.

² Vital signs include systolic and diastolic pressure in mmHg, respiratory rate/minute, heart rate/minute and temperature.

³ Height measured at Screening Visit only.

⁴ Screening labs include uric acid, urinalysis and Serum pregnancy test (WOCBP) and will be performed at local institution.

Inosine in ALS

V3.0

7/01/2019

⁵ Uric acid level will be measured just before the first dose (Baseline visit) or just before scheduled morning dose (trough) (Weeks 3, 6, 9, 12, 16, 20) (Quest Diagnostics)

⁶ Urinalysis with sediment (Quest Diagnostics)

⁷ Safety labs include Hematology (CBC with differential), Basic Metabolic Panel, Liver Function Tests and will be performed at local institution.

⁸ Pulmonary Function Testing includes Slow Vital Capacity (SVC)

⁹ Adverse events that occur AFTER signing consent form will be recorded.

¹⁰ App installation and un-installation procedures include a brief survey about phone use

STUDY WORKFLOW

[figure not shown]
Screening Period

On Active Treatment

Washout Period

[figure not shown]
[figure not shown]
~ 60 Screened

15 Subjects on inosine (administered as 500 mg caps; 1 to 6 caps a day; dose titrated to target urate levels of 7 - 8 mg/dL).

15 Subjects on placebo (administered as 500 mg caps; 1 to 6 caps a day; pseudo-titration will be performed to maintain blinding).

21 Days

Subjects who discontinue from the study early will be asked to return to the study site for Final Safety assessments, and will be asked to have a final Follow-Up Telephone Call 28 days (+5 days) after taking their last dose of study drug.

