4 STUDY DESIGN

4.1 Overall Study Design and Plan

During the enrollment period, approximately 60 subjects will be screened at up to three (3) Northeast ALS Consortium (NEALS) Centers in the United States. Approximately 30 of these subjects are expected to be found eligible for study enrollment and will be randomized 2:1 to receive inosine or placebo. Per study protocol, the aim is to elevated serum urate levels only in those subjects whose baseline urate level falls below the predicted median for this population. Approximately 30 subjects will receive inosine or placebo for 20 weeks (administered in the form of 500 mg capsules, 1 to 6 capsules a day for a total daily dose of up to 3 gm). The dose of inosine will be titrated to target urate levels of 7-8 mg/dL based on urate level measurement that will occur at the Week 3, Week 6, Week 9, Week 12 and Week 16 visits. Clinic visits will occur at Screening, Baseline, Week 12, Week 20 and Unscheduled Safety Visits. Telephone visits and remote serum urate testing will occur at Week 3, Week 6, Week 9 and Week 16. There will be a window of ± 3 days for each visit. The Screening Visit must be completed within 21 days of the Baseline Visit. All visit windows are consecutive calendar days and are calculated from the day the participant starts study treatment (Day 0, the day of the Baseline Visit).

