5 SELECTION AND WITHDRAWAL OF STUDY POPULATION

5.1 Number of Study Subjects

Approximately 60 subjects will be consented for the study. Any subject who signs consent will be considered enrolled in the study. Screening study procedures will begin after informed consent.

We expect a 50% screen fail rate based on our goal of elevating serum urate levels only in those subjects whose serum urate level falls below the population median. This subpopulation is at greater risk of faster disease progression and can also accommodate an increase in serum urate to higher, but still normal levels, which are known to be associated with slower disease progression^{21, 31, 35}.

Thirty (30) subjects will receive inosine or placebo for 20 weeks per study protocol and will be followed up to Week 24.

If a subject fails screening, at a minimum, the following information will be captured and entered in the data capture system: inclusion/exclusion criteria, demographics, screening lab results, reason for screen failure.

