10.2.2.5 Power Calculations

Assuming that 50%, 20%, and 10% of participants in the placebo group are expected to experience an AE or a given type of AE, we will have 80% power to declare a significant treatment-dependent increase in the proportion experiencing an AE if at least 95%, 71%, and 59% of participants in the inosine group are expected to experience an AE, respectively. We will have 80% power to observing at least one instance of any inosine-associated AE with a true probability of occurrence of at least 8%. For tolerability, we will have 80% power to declare inosine tolerable if the true proportion tolerant is at least 71%. Variance component estimates for calculating power for effects of treatment on ALSFRS-R are from a single arm pilot study of 25 participants on inosine for 20 weeks. Based on the follow-up schedule for this trial and assuming a random-slopes model, the estimated effective SD for ALSFRS-R slope per month is 1.4. Given this estimate, we will have 80% power to detect a difference in ALSFRS-R slopes between the inosine and placebo groups of 1.05 units per month. We will have 12% power for a difference in slopes of 0.3 units per month.

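### Arm sizes contradict: the Study Workflow shows 15 inosine and 15 placebo, but Section 4.1 randomises about 30 subjects 2:1, and the 8% event-detection claim fails with 15 on inosine

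*Combined protocol and SAP*

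**What the plan says.** - **Study Workflow (Protocol Summary):** "15 Subjects on inosine" and "15 Subjects on placebo".
- **Section 4.1:** about 30 of the screened subjects are expected to be eligible and "will be randomized 2:1 to receive inosine or placebo". It adds: "Approximately 30 subjects will receive inosine or placebo for 20 weeks".
- **Section 5.1:** "Thirty (30) subjects will receive inosine or placebo for 20 weeks". This gives the total only, with no split.
- **Section 10.2.2.1:** adverse event proportions are compared by one-tailed Fisher's exact tests at alpha 0.05.
- **Section 10.2.2.5:** "Assuming that 50%, 20%, and 10% of participants in the placebo group are expected to experience an AE" or a given type of AE, the trial is said to have 80% power "if at least 95%, 71%, and 59% of participants in the inosine group are expected to experience an AE", respectively. It also claims 80% power to observe "at least one instance of any inosine-associated AE with a true probability of occurrence of at least 8" per cent. No arm sizes are given.
- **Section 5.3:** subjects who withdraw are not replaced.

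**The concern.** Two groups of 15 are not a 2:1 allocation at any total, so the word approximately in Section 4.1 cannot reconcile the statements. Both are legible text of the current version, and neither is given precedence over the other.

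The number of subjects on inosine matters because the primary objective is the safety and tolerability of inosine. It fixes the exposure on which rare events could be seen, and it fixes the precision of the single-proportion tolerability rule in Section 10.2.2.2. Fifteen rather than 20 is a quarter less exposure (5/20). Because Section 10.2.2.5 names no arm sizes, a reader cannot tell from the text which split the power claims assume.

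**Working it through.** **Inputs.** Total 30 (Sections 4.1, 5.1). Candidate splits: 20 inosine and 10 placebo (2:1 of 30, Section 4.1), or 15 and 15 (Study Workflow). Test: one-tailed Fisher, alpha 0.05 (Section 10.2.2.1). Placebo rates 50%, 20%, 10%; printed inosine rates 95%, 71%, 59%; event probability 8% (Section 10.2.2.5).

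**1. Event detection.** P(at least one event) = 1 − (1 − p)^n with p = 0.08.

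- n = 20: 1 − 0.92^20 = 1 − 0.1887 = 0.811. This reproduces the printed claim.
- n = 19: 1 − 0.92^19 = 0.795, just short of 80%.
- n = 15: 1 − 0.92^15 = 1 − 0.2863 = 0.714.

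Smallest n for 80%: ln(0.2)/ln(0.92) = 19.3, so 20 subjects. Conversely, the rate seen at least once with 80% probability is 1 − 0.2^(1/n): 7.7% at n = 20, which rounds to the printed 8%, and 10.2% at n = 15.

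**2. Between-arm comparisons.** For every pair of event counts (a on inosine, b on placebo), the one-tailed Fisher p-value was computed. Power is the sum of the binomial probabilities of the pairs with p ≤ 0.05. The threshold is the inosine rate at which power equals 80%.

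| Placebo rate | Printed inosine rate | Power at printed rate, 20:10 | Threshold, 20:10 | Power at printed rate, 15:15 | Threshold, 15:15 |
|---|---|---|---|---|---|
| 50% | 95% | 79.7% | 95.1% | 84.3% | 93.7% |
| 20% | 71% | 80.1% | 71.0% | 82.4% | 69.6% |
| 10% | 59% | 79.7% | 59.1% | 83.1% | 57.0% |

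At 20:10 all three thresholds round to the printed figures. At 15:15 none does. The trial would then have slightly more than the stated power at the printed rates, so the printed rates would no longer be the 80% thresholds.

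**3. Tolerability, for consequence only.** Section 10.2.2.2 requires a one-sided 95% lower bound above 50% but names no method for the bound. Assuming an exact (Clopper-Pearson) bound:

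- n = 20: 15 tolerant subjects are needed (bound 0.544; 14/20 gives 0.492). 80% power requires a true rate of 79.9%.
- n = 15: 12 are needed (bound 0.560; 11/15 gives 0.489). 80% power requires a true rate of 84.3%.

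The printed 71% for tolerability is not used to decide between the splits. With an exact bound its power is 45.5% at n = 20 and 32.7% at n = 15, so it fails at both sizes and is a separate error. The ALSFRS-R power figures are not used here either.

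**The case against.** The best counter-argument is that this is one stale diagram. The design section states 2:1, and the safety power figures were evidently computed for 20 and 10. At that split the 8% claim is correct, so the power section contains no error on this point. If 15:15 were used, all three Fisher claims would still be met, the total of 30 would be unchanged, and only the 8% figure would newly fail. A wrong label by itself changes neither exposure nor power; that would need somebody to randomise from the diagram.

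Most of this stands. The evidence does favour 2:1, and the 8% claim fails only if the Workflow is right. It does not remove the point: no section states 20 and 10, no section gives either statement precedence, and the document cannot show what the randomisation list contains. It is also fair that the tolerability thresholds depend on an assumed exact bound, and that they describe a consequence rather than evidence for either split.

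**Conclusion.** The concern holds. The protocol states two incompatible allocations. Four figures in Section 10.2.2.5 match 20:10 and none is reproduced by 15:15, so the Workflow is the likely error.

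If 15:15 were the real design, inosine exposure would be a quarter lower and the chance of seeing an 8% event would be 71.4% instead of 81.1%. The tolerability criterion would also be harder to meet: 84.3% instead of 79.9% true tolerance for 80% power, given an exact bound. The between-arm Fisher comparisons would gain about 2 to 5 percentage points of power.

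These figures assume exactly 30 treated subjects, all contributing to the analysis. At 2:1 there is no margin for the 8% claim: with 19 on inosine the probability is already 79.5%. The correction should be made, but it does not call the trial's design into question if the list is 2:1.

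**What to change.** Check the allocation in the randomisation list, then do one of the following.

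- **If it is 2:1:** change the Study Workflow to 20 subjects on inosine and 10 on placebo, and write 20 and 10 explicitly in Sections 4.1, 5.1 and 10.2.2.5. The printed safety power figures can stay. The cost is protocol wording only.
- **If it is 1:1:** change Section 4.1, state 15 and 15 in Sections 5.1 and 10.2.2.5, restate the 8% detection figure as about 10%, and restate the three Fisher thresholds as about 94%, 70% and 57%. The edits are again wording, but if subjects have already been randomised 1:1, the departure from Section 4.1 would also need to be documented.

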1 ETHICS/PROTECTION OF HUMAN SUBJECTS

1.1 Institutional Review Board (IRB)

This study will be conducted in compliance with current Good Clinical Practices (GCP) and Title 21 Part 56 of the United States of America Code of Federal Regulations (CFR) relating to IRBs.

1.2 Ethical Conduct of Study

The study will be conducted in accordance with GCP defined by the International Conference on Harmonization (ICH) and the ethical principles of the Declaration of Helsinki.

1.3 Subject Information and Consent

This study will be conducted in compliance with Title 21 Part 50 of the United States of America Code of Federal Regulations (CFR), Federal Regulations and ICH Guidance Documents pertaining to informed consent. At the first visit, prior to initiation of any study-related procedures, subjects will be informed about the nature and purpose of the study, participation/termination conditions, and risks and benefits. Subjects will be given adequate time to ask questions and become familiar with the study prior to providing consent to participate. Subject will give their written consent to participate in the study and will be provided with a copy of the fully executed consent form for their records.

2 INTRODUCTION: BACKGROUND INFORMATION AND SCIENTIFIC RATIONALE

2.1 Background Information

2.1.1 Clinical Features and Epidemiology of ALS

Amyotrophic lateral sclerosis (ALS) is a rare degenerative disorder of large motor neurons of the cerebral cortex, brain stem and spinal cord that results in progressive wasting and paralysis of voluntary muscles¹. The incidence of ALS is currently approximately 2/100,000². The lifetime ALS risk is 1 in 600 to 1 in 1000². Even though the incidence of ALS is similar to that of multiple sclerosis, the prevalence is only 4- 6/100,000 (about 25,000-30,000 subjects in the United States), due to the higher mortality rate. Fifty per-cent of ALS cases die within three years of onset of symptoms and 90% die within five years³. The median age of onset is 55 years³. The cause in most cases is unknown⁴. Age and male gender are the only risk factors repeatedly documented in epidemiological studies. No treatment prevents, halts or reverses the disease, although the use of riluzole (the only FDA-approved therapy for ALS) is associated with a slight prolongation of survival⁵.

2.1.2 Role of oxidative stress in ALS Pathogenesis

Despite decades of focused research, a unifying and well-tested theory of ALS disease pathophysiology remains enigmatic⁴. At the same time, the body of knowledge has expanded dramatically as research tools have improved. Research increasingly implicates oxidative stress as one of the major molecular mechanisms leading to neuronal death in ALS⁶.

Oxidative stress has been implicated in the pathophysiology of ALS since the discovery that mutations in an antioxidant system, the copper/zinc superoxide dismutase (Cu/Zn SOD, SOD1) gene, are associated with 20% of cases of familial ALS^{7, 8}. Identification of SOD1 as the first gene linked to ALS pathophysiology has enabled the development of animal models from which much of our understanding of the mechanisms of neurodegeneration in ALS has emerged. These studies have shown that the neurodegenerative processes involved in this disease are diverse and complex including not only oxidative stress, but also excitotoxicity, mitochondrial dysfunction, defects in RNA processing, inflammation, protein aggregation, disruption of neurofilaments and intracellular trafficking along microtubules, as well as involvement of non-neuronal cells in the vicinity of motor neurons^{8, 9}. Nevertheless, oxidative stress, whether as a primary cause of disease or a secondary consequence, has been implicated in many of these processes and appears as a central mechanism by which motor neuron death occurs⁷.

Despite the compelling evidence supporting a pathogenic role of oxidative stress in ALS, the agents with antioxidant properties studied to date (such as CoQ10 and Vitamin E)^{10, 11} in randomized placebo-controlled clinical trials have failed to show benefits on disease progression. This observation highlights the fact that it is important to include assessment of measures of target engagement in the study design of pilot, proof-of-concept studies of candidate compounds in order to demonstrate the intended biological effect in early studies prior to proceeding along the drug development process.

2.2 Rationale for choosing inosine for ALS

Inosine is an intermediary metabolite of purine metabolism, is available as an over-the-counter oral supplement. Inosine is converted into urate, the anionic form of uric acid (Fig. 1).

Urate may be one of our major endogenous defenses against oxidative stress. As an apparent consequence of multiple independent mutations in the *urate oxidase* gene (*UOx*) during primate evolution¹²⁻¹⁴, urate circulates at high concentrations near the limits of its solubility (accounting for our susceptibility to gout) and constitutes the end product in the metabolism of purines in humans and apes (Fig. 1). The demonstration that urate possesses antioxidant properties comparable to those of ascorbate^{13, 15} and accounts for most of the antioxidant capacity in human plasma^{16, 17}, supports the hypothesis that our ancestors gained antioxidant benefits from *UOx* mutations and the resulting urate elevation^{18, 19}.

[figure not shown]

Figure 1.
Purine metabolism

Interestingly, urate has been gaining momentum as a promising agent for neuroprotection based on rapidly accumulating epidemiological observations, laboratory data, and early clinical trial results in multiple neurologic diseases, most notably Parkinson disease (PD)^{20, 21}. These lines of evidence (summarized below) demonstrate the potential therapeutic significance of unraveling the molecular mechanisms of urate actions in the CNS and have already prompted clinical development of urate-elevating strategies for PD²¹ and stroke²².

